5.1.5.2 Analysis of Reduction in Bowel Movements

An analysis of the proportion of patients reporting a reduction in bowel movements will be conducted at the 6-month Follow-up. This endpoint is not described in the study protocol. For the main analysis of this endpoint, the proportion of patients who respond that the number of bowel movements since starting XERMELO is "A great deal better," "Much better," or "A little better" will be computed. As a supplemental analysis, the proportion of patients who respond that the number of bowel movements is "A great deal better" or "Much better" only will be computed.

5.1.5.3 Subgroup Analyses

Subgroup analyses of study endpoints based on categories of sociodemographics or clinical characteristics of patients may be conducted on a post hoc basis. These analyses will not be prespecified in this statistical analysis plan, and will be considered exploratory in nature.

5.1.5.4 Exploratory Analyses

Exploratory analysis of the association between patient satisfaction with overall CS symptom control at the initial 6-month Follow-up and the incidence of at least 1 ER visit, at least 1 hospitalization, and mortality will be performed as part of the final analysis. Only patients with non-missing data on satisfaction with overall CS symptom control at 6 months

will be included in the analysis. The satisfaction categories correspond to the binary categories used in the main analysis of the primary endpoint.

- Contingency table analysis to compare the incidence proportions of ER visits, hospitalizations, and mortality for each Follow-up interval and for the entire study period by satisfaction category, with chi-square tests for association. The satisfaction categories correspond to the binary categories used in the primary endpoint.
- Logistic regression models for the incidence of at least 1 ER visit and/or at least 1 hospitalization during the study period, with satisfaction category as a predictor variable. Covariates may be included in the models.

Additional or alternative exploratory analyses to be performed after data collection is complete will be determined in consultation with Lexicon and described in the final study report. The feasibility of each additional analysis will depend on the extent of data availability. Examples of additional analyses that may be considered are as follows:

- Kaplan-Meier analysis of mortality data, stratified by satisfaction category, including log-rank tests for differences between the strata.
- Kaplan-Meier analysis of time to first hospitalization, first ER visit, or mortality.
- Cox models for times to first ER visit, first hospitalization, and mortality, with satisfaction category as a predictor variable. Covariates may be included in the models.

Statistical tests will be 2-sided and have an associated alpha level of 0.05. The p-values from these tests will be considered descriptive rather than inferential.

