Methodology	
This observational, noninterventional, single-arm study will include patients with CS and who are initiating treatment with XERMELO. Patients will be asked to complete up to 7 web-based surveys including a Baseline assessment and then every 6 months for a total of up to 3 years. Each survey is anticipated to take no more than 20 minutes on average. All assessments, except mortality, will be patient-reported; medical records will not routinely be requested or reviewed as part of this observational study unless required for safety reporting purposes.
 
XERMELO prescription fill data will be collected directly from the specialty pharmacies, for all study patients that enter this study.
 
Upon entering the study, patients will be asked to provide sociodemographic information, current medical history (specifically date of CS and neuroendocrine [NET] diagnosis, NET location, CS-related hospitalization and/or ER visits, and NET-related surgery), height, weight, concomitant medications (specifically those related to SSA therapy, systemic therapy, and liver-directed therapy). In addition, patients will be asked to complete a work productivity and activity impairment (WPAI) assessment and describe satisfaction with CS, CS-related diarrhea and/or flushing prior to initiating treatment with XERMELO.
 
Patients will complete a survey every 6 months, describing changes to previously reported data and/or new occurrence of pre-specified events.
 
Data that may be collected at the 6 month time point includes changes in weight, concomitant medications (specifically those related to SSA therapy, systemic therapy, and liver-directed therapy), WPAI assessment, and satisfaction with CS, CS-related diarrhea and/or flushing following the initiation of treatment with XERMELO, as well as, new occurrence(s) of CS-related hospitalization and/or ER visit(s) will also be collected.
 
Following the month 6 time point, long-term assessments are to include changes in weight, concomitant medications (specifically those related to SSA therapy, systemic therapy, and liver-directed therapy), as well as, new occurrence(s) of CS-related hospitalization and/or ER visit(s) will also be collected.
 
Throughout the study information related to mortality will be collected through indirect sources.

Number of Patients	A minimum of 643 patients with CS who initiate treatment with XERMELO are expected to participate in this study.

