10.4.1 Analyses of Study Endpoints

For the primary endpoint, the proportion of CS patients who are at least somewhat satisfied with their overall symptom control at 6 months, a point estimate and the corresponding 95% CLs will be calculated. Secondarily, a point estimate and corresponding 95% CLs will be calculated for the proportion of CS patients who are very satisfied with their overall symptom control at 6 months. The 95% CLs will be unadjusted and based on the assumption of approximate normal distribution. Missing data will not be imputed in the main analysis of the primary endpoint. As a sensitivity analysis, a patient with a missing response at 6 months will be imputed as a non-responder. This approach corresponds to non-responder imputation.

In addition to the point estimates and 95% CLs for the primary endpoint, the frequency distribution of the categorical responses, on a 5-point Likert scale, to patient satisfaction with overall symptom control at 6 months will be presented. The patient satisfaction measure will also be summarized as an ordinal variable with a value of 1 corresponding to “very dissatisfied” up to 5 corresponding to “very satisfied”.

All the secondary endpoints correspond to proportions and will be summarized through point estimates and 95% CLs, as described above for the primary endpoint. Frequency distributions of the categorical responses and summary statistics of the corresponding ordinal values of the categories will be presented. The handling of patients with a response of “not applicable” to patient satisfaction with CS-related diarrhea control or patient satisfaction with CS-related flushing control in the analysis will be described in the SAP.

The 4 WPAI-SHP scores at Baseline and month 6 will be summarized, as well as the change from Baseline to month 6.

The incidences of at least 1 CS-related hospitalization, at least 1 CS-related ER visit, and mortality after Baseline will be calculated at each 6-month interval. Kaplan-Meier estimates of each time-to-event variable, including quartiles, medians, and their corresponding 95% CLs, will be presented. The association or relationship between the primary endpoint and each long-term health outcome will be evaluated through descriptive statistics and the use of statistical models, as appropriate. Any statistical models that will be used and the appropriateness and/or limitations of their use will be described in the SAP.

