2.2.2 Secondary Objectives

The following secondary objectives will be assessed 6 months after initiating treatment with telotristat ethyl (XERMELO):

- To estimate the proportion of patients reporting satisfaction of CS-related diarrhea control
- To estimate the proportion of patients reporting satisfaction of CS-related flushing control
- To estimate the proportion of patients reporting reduction in rescue SSA use

- To estimate the proportion of patients reporting reduction in the dose of long-acting SSA injection
- To estimate the proportion of patients reporting reduction in the frequency of long-acting SSA injection
- To estimate the proportion of patients reporting an overall improvement in CS control after initiating XERMELO based on the Patient Global Impression of Change (PGIC)
- To estimate the proportion of patients who had reduction in work-related absenteeism, presenteeism, activity impairment, and overall productivity loss after initiating XERMELO based on Work Productivity and Activity Impairment Questionnaire: Specific Health Problem v.2.0 (WPAI-SHP)
- To estimate the proportion of patients reporting weight gain

2.2.3 *Exploratory Objectives*

To explore the association between satisfaction with overall and CS symptom control (ie, diarrhea, flushing) at month 6 and long-term health outcomes such as, CS-related hospitalization, CS-related emergency room (ER) visits, and mortality over the study period

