3.2.3 Symptom Control

Satisfaction with control of diarrhea, flushing, and overall CS symptoms will be assessed at Baseline. Satisfaction with how XERMELO has controlled diarrhea, flushing, and overall CS symptoms will be assessed at the initial 6-month Follow-up only. The questionnaire items allow patients to choose a response on a 5-level Likert scale ranging from "Very dissatisfied" (level 1) to "Very satisfied" (level 5). For the assessments of satisfaction with control of diarrhea and flushing, "Not applicable" (level 0) is also 1 of the response options, for those patients who do not have the symptom that is being assessed.

At the initial 6-month Follow-up, patients will also be asked to assess the change in the number of bowel movements on a 7-level Likert scale from "A great deal worse" to "A great deal better." This assessment is not described in the study protocol.

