3.2.5 Work Productivity and Activity Impairment Questionnaire—Specific Health Problem (WPAI-SHP)

The WPAI-SHP is a self-administered questionnaire ([Reilly et al., 1993](#)) comprising 6 questions that measure the effect of health problems on participants' ability to work and participate in regular activities based on their experiences in the previous 7 days. This questionnaire will be administered at Baseline and at the initial 6-month Follow-up.

The WPAI-SHP includes 4 domains (absenteeism, presenteeism, work productivity loss, and activity impairment). All participants will be asked whether they are employed (Q1) and how their CS-related problems affected their regular activities (Q6). Employed participants will be asked about hours of work missed due to CS-related problems (Q2), hours of work missed for any reason (eg, vacation, holidays, time off to participate in this study) (Q3), hours actually worked (Q4), and the degree that CS affected their productivity while working (Q5). An integer scale from 0 to 10 is used for Q5 and Q6, where 0 corresponds to no effect and 10 corresponds to complete effect.

Responses to the items are scored to produce the following 4 domains:

- Absenteeism: work time missed due to CS = [REDACTED]
- Presenteeism: impairment while working due to CS = [REDACTED]

- Work productivity loss: overall work impairment due to CS = [REDACTED]
[REDACTED]
- Activity impairment: activity impairment due to CS = [REDACTED]

Each score is then multiplied by 100 to express domains in terms of impairment percentages, with higher numbers indicating greater impairment and less productivity (ie, worse outcomes).

3.2.6 *Carcinoid Syndrome-related Health Care Resource Utilization*

At Baseline and at each Follow-up, questionnaire items will ask patients about ER visits and hospitalizations during the prior 6-month period. Data collected will include the following:

- The number of ER visits and the CS-related reason for each visit
- The number of hospitalizations, the number of nights for each stay, and the CS-related reason for each hospitalization

3.2.7 *Study Discontinuation and Mortality*

Patients will be terminated from the study if they discontinue the use of XERMELO, withdraw consent for participation, or are lost to follow-up. Information on reasons for discontinuation will be provided by the specialty pharmacy.

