5 STATISTICAL ANALYSIS

5.1 Statistical Methods

5.1.1 General Considerations

Derivation of analytic variables will be detailed in a separate analytic variable specification document to be produced in Microsoft Excel. This document will be developed at the time of the first interim analysis and will be maintained through the final analysis. It will be provided to Lexicon at the end of the study, along with the corresponding SAS data sets.

All analyses will be descriptive in nature. For continuous and ordinal variables, the number of available observations, means, standard deviations (SDs), medians, minimums, and maximums will be provided. For categorical variables, the frequency and percentage in each category will be displayed. For computation of percentages, missing values and "Prefer not to answer" responses will not be included in the denominator. Results will be presented by study time point, where applicable. Additionally, all questionnaire data will be displayed in listings. Height and weight information will be collected in feet and inches and in pounds but will be summarized in the tables in centimeters and kilograms, respectively. By convention, dates will be displayed in DDMMYYYY format (eg, 17JAN2017). For the times since diagnosis of CS and diagnosis of primary NET and all time-to-event analyses, the date of Baseline questionnaire completion will be considered as Day 1, and times will be expressed in months or years, as appropriate. The day before the date of Baseline questionnaire completion will be considered Day -1; there will be no Day 0.

All analyses will be performed in SAS, Version 9.4 or higher (SAS Institute, Cary, NC).

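### The pooled table and the logistic models count ER visits and hospitalizations from before the month-6 satisfaction answer as outcomes of that answer

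*SAP*

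**What the plan says.** - **Predictor.** SAP 3.2.3: satisfaction with control on XERMELO "will be assessed at the initial 6-month Follow-up only".
- **Outcome data.** SAP 3.2.6: at Baseline and each Follow-up, "questionnaire items will ask patients about ER visits and hospitalizations during the prior 6-month period". The month-6 survey therefore collects the answer and the events of months 0-6 together.
- **Analyses.** SAP 5.1.5.4 plans a contingency table for each Follow-up interval and "for the entire study period by satisfaction category, with chi-square tests for association". It also plans "Logistic regression models for the incidence of at least 1 ER visit and/or at least 1 hospitalization during the study period", with satisfaction as predictor and covariates optional. Only patients with a month-6 answer enter.
- **Clock.** SAP 5.1.1: for "all time-to-event analyses, the date of Baseline questionnaire completion will be considered as Day 1". Protocol 10.4.1 counts these events after Baseline, and Protocol 10.3.2 and SAP 2.3.3 count them for up to 3 years after initiation.
- **Objective.** SAP 2.2.3 names "long-term health outcomes such as, CS-related hospitalization, CS-related emergency room (ER) visits, and mortality over the study period". The Protocol synopsis (Methodology) uses the term differently: "Following the month 6 time point, long-term assessments are to include changes in weight".
- **Limitations.** Protocol 10.4.1: "Any statistical models that will be used and the appropriateness and/or limitations of their use will be described in the SAP". SAP 5.1.5.4 states none about timing.

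**The concern.** A patient hospitalized in month 3 may be less satisfied in month 6 because of it. Both pooled analyses would then show fewer events among satisfied patients, even if satisfaction carried no information about what follows. Adjustment cannot repair this while the early event is part of the outcome.

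Protocol 3.2 states the sponsor's assumption that satisfied patients stay on XERMELO and so do better in the long term. Reverse ordering pushes the pooled result in just that direction.

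The problem is confined to ER visits and hospitalizations. Anyone who answers at month 6 was alive then, so deaths do not have the reverse order. The tables for intervals 2-6 are correctly ordered. The first-interval table is not, but it stands alone and needs only a label.

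**Working it through.** **1. The plan's own figure.** SAP 2.4 needs 1.96² × 0.5 × 0.5 / 0.05² = 384.15, so 385 month-6 responders. This agrees, and n = 385 is used below. Inflating for 40% dropout gives 385 / 0.60 = 641.7, so 642 against the stated 643; the difference has no bearing here. The plan gives no figure for the association itself.

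**2. Share of counted events that come first.** With constant assumed risk q per interval, independent across intervals, the share of patients with any event over K intervals who already had one in months 0-6 is q / (1 − (1 − q)^K). For q from 5% to 20% this is 51%-56% at 12 months (K = 2) and 19%-27% at 36 months (K = 6).

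**3. Model with no effect of satisfaction on later events.** E is an event in months 0-6, S is satisfied at month 6, and L is an event in the k intervals after month 6 (k = 1 for 12 months, k = 5 for 36 months). All inputs except n are assumed: P(E) = 0.10; P(S | no E) = 0.55; P(S | E) = s = 0.25, 0.35 or 0.45; complete follow-up. S depends only on E.

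Example, s = 0.25, independent risk:
- P(S) = 0.9 × 0.55 + 0.1 × 0.25 = 0.52
- P(E | S) = 0.025 / 0.52 = 0.0481; P(E | not S) = 0.075 / 0.48 = 0.1563
- Any event by 12 months: 1 − 0.9519 × 0.9 = 0.1433 if satisfied; 1 − 0.8438 × 0.9 = 0.2406 if not
- Odds ratio (satisfied vs not) = (0.1433 / 0.8567) / (0.2406 / 0.7594) = 0.528; the true value for later events is 1

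**4. Persistent patient risk.** If each patient's risk is beta-distributed with mean 0.1, then P(no L | E) and P(no L | no E) follow from Beta(a+1, b) and Beta(a, b+1). For a+b = 2 and k = 5 they are 0.2116 and 0.7993. With s = 0.25:
- Entire period: 1 − 0.9519 × 0.7993 = 0.2391 against 1 − 0.8438 × 0.7993 = 0.3256; OR 0.651
- From month 6, unadjusted: 0.0481 × 0.7884 + 0.9519 × 0.2007 = 0.2289 against 0.1563 × 0.7884 + 0.8438 × 0.2007 = 0.2925; OR 0.718

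**5. Results.** Odds ratios are exact. Rejection at two-sided 0.05 comes from 20,000 simulated studies per cell. Values are for s = 0.25 / 0.35 / 0.45.

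| Risk, horizon | Outcome window | OR | Rejection, % |
|---|---|---|---|
| Independent, 12 months | Entire period | 0.528 / 0.655 / 0.810 | 68.3 / 36.4 / 13.0 |
| Independent, 36 months | Entire period | 0.774 / 0.842 / 0.918 | 24.5 / 13.4 / 7.4 |
| a+b = 5, 36 months | Entire period | 0.713 / 0.798 / 0.893 | 35.6 / 18.9 / 8.2 |
| a+b = 5, 36 months | From month 6, unadjusted | 0.830 / 0.883 / 0.939 | 14.0 / 9.2 / 5.9 |
| a+b = 2, 36 months | Entire period | 0.651 / 0.751 / 0.867 | 46.7 / 24.1 / 9.6 |
| a+b = 2, 36 months | From month 6, unadjusted | 0.718 / 0.802 / 0.895 | 28.9 / 16.0 / 7.5 |

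With the window from month 6 and E as stratum or covariate, the median adjusted odds ratio is 1.00-1.01 in every cell. Rejection is 4.6%-5.2% (Cochran-Mantel-Haenszel) and 4.8%-5.5% (logistic likelihood-ratio test). If early events do not change satisfaction (s = 0.55), the unadjusted tests reject in 4.6%-5.2%.

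**6. Limits of the remedy** (a+b = 2; 10,000 runs). If satisfaction follows the patient's underlying risk directly (s = 0.35, 36 months), the adjusted odds ratio is still 0.59 (54% rejection), or 0.64 (37%) with the pre-Baseline event added. If 90% of satisfied and 70% of other responders continue, 309-311 of 385 remain. The stratified odds ratio stays 1.00 when continuation depends on satisfaction only. It becomes 1.40 at 12 months and 1.29 at 36 months (10.5%-13.2% rejection) when high-risk dissatisfied patients also stop more often.

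**The case against.** - **The start at Baseline is inferred.** SAP 5.1.5.4 does not define the study period. The Day 1 rule covers time-to-event analyses, which a chi-square table and a logistic model are not, and variable derivations sit in a separate specification outside these documents. This stands as a caution. But every related section counts from Baseline or initiation, and none points to month 6. Restricting to month-6 responders selects patients without moving the start of the count.
- **The aim may not be prospective.** The SAP promises only to explore an association, and the Protocol's exploratory objective is not visible. That weakens the argument from the term long-term. The time order remains wrong for an objective about long-term outcomes.
- **Correctly ordered tables are already planned, and p-values are descriptive.** True, and this limits the severity. Those tables do not correct the pooled table or the models, and a descriptive label does not reverse the time order.
- **The size is assumed, and the fix is imperfect.** Also true. The 68% figure needs a 30-point fall in satisfaction and outcomes ending at 12 months. When risk persists, moving the window alone helps only partly, and the rest is confounding by patient risk. Residual confounding or selective stopping can bias the corrected analysis in either direction.

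**Conclusion.** The concern holds. As written, the entire-period table and the logistic models mix the wanted association with its reverse. That conclusion rests on the text and on reading the study period as starting at Baseline.

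The size cannot be derived from the documents. Under the stated assumptions the spurious odds ratio at 36 months runs from 0.65 (strongly persistent risk, large fall in satisfaction) to 0.92 (independent risk, small fall). It is larger at shorter follow-up: 0.53-0.81 at 12 months even with independent risk. If early events leave satisfaction unchanged, there is no distortion.

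This should be fixed before the final analysis, where SAP 4.2 schedules the exploratory work.

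**What to change.** 1. In SAP 5.1.5.4, start the outcome window at the month-6 survey for the entire-period table, the logistic models and any later Kaplan-Meier or Cox analysis by satisfaction, among responders with some follow-up after it. Align the objective in SAP 2.2.3.
2. Make the month 0-6 event a required covariate in the models. Stratify the pooled table by it (Cochran-Mantel-Haenszel), or state that the table is not adjusted for persistent patient risk. The event in the 6 months before Baseline, already collected, is an optional second covariate.
3. Keep the first-interval ER and hospitalization table and label it cross-sectional.
4. As a side point, SAP 3.2.7 allows deaths to arrive as aggregated counts, which cannot be linked to satisfaction. State that mortality by satisfaction is analysed only with patient-level deaths.
5. State the remaining limits, as Protocol 10.4.1 foresees: association only, in a set selected on continued XERMELO use.

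**Cost.** SAP wording, a changed window and one covariate or stratum, with no new data collection. There are fewer events, and responders without later follow-up drop out; under Protocol 6 the last patient enrolled completes only Baseline and month 6. The remaining set is selected on continued use (Protocol 5.1.1), as the planned tables for intervals 2-6 already are. Unequal follow-up after month 6 is a separate matter that this change does not address.

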5.1.1 Survey Conduct

An electronic consent and survey questionnaire approved by an Institutional Review Board (IRB) will be used by RTI to program the online survey for the purpose of standardizing responses among patients.

Each patient will complete up to 7 web-based surveys over the duration of the study. Each survey is anticipated to take no more than 20 minutes on average.

All assessments, except mortality, will be patient-reported; medical records will not routinely be requested or reviewed as part of this observational study unless required for safety reporting purposes. As patient recall over time may be limited, partial responses as in the case of dates of onset, and/or estimates of numerical information will be accepted.

Participation in the study is contingent on continued use of XERMELO. Each survey will establish ongoing treatment with XERMELO and continued consent to study participation prior to subsequent data collection.

The initial survey is intended to gather Baseline information, which may include:

- Sociodemographics (age, year of birth, sex, race, ethnicity, education, geographic region)
- Current medical history as it relates to CS, NET burden, NET location, and related conditions
 - Location of NET
 - Date of diagnosis; CS and NET
 - CS-related hospitalization(s)
 - CS-related ER visit(s)
 - NET-related surgery (eg, tumor debulking, lysis of adhesions)
- Satisfaction with CS, CS-related diarrhea and/or flushing control prior to starting XERMELO, where applicable
- Height and weight
- Concomitant medication as it relates to the following:
 - Long-acting SSA therapy

- Use of rescue medication - short-acting SSA
- Systemic tumor-directed therapy
- Liver-directed therapy (eg, chemoembolization)
- WPAI-SHP

The initial survey should be completed no later than 30 days, and subsequent surveys should be completed no later than 14 days, after the unique survey link has been provided to the patient via e-mail. Patients will be asked to complete a survey every 6 months for up to 3 years. The following patient-reported data may be collected as described in [Appendix A](#):

- Satisfaction with CS, CS-related diarrhea and/or flushing control after initiating XERMELO, where applicable
- PGIC
- Concomitant medication as it relates to the following:
 - Change in use of rescue medication - short-acting SSA
 - Change in long-acting SSA therapy
 - Systemic tumor-directed therapy
 - Liver-directed therapy (eg, chemoembolization)

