5.2 Missing Data

No imputations will be performed, except as noted for the sensitivity analysis for the primary endpoint as described in Table 1 ([Section 5.1.4](#)). In all other cases, missing data will be excluded and variables will be analyzed using the available observed data.

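### SAP 5.1.5.4: the whole-period chi-square test and logistic model of ER visits and hospitalizations by month-6 satisfaction ignore time at risk, so they are biased under plausible scoring rules if follow-up depends on satisfaction

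*SAP*

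**What the plan says.** SAP 5.1.5.4 limits the exploratory analyses to patients with a month-6 response on overall satisfaction and splits them into the two primary-endpoint categories. It then commits to two analyses:

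- contingency tables "for each Follow-up interval and for the entire study period by satisfaction category, with chi-square tests for association";
- "Logistic regression models for the incidence of at least 1 ER visit and/or at least 1 hospitalization during the study period", with satisfaction category as predictor.

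Cox models by satisfaction appear in the same section, but only among examples that may be considered.

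Other sections bear on how these would be computed:

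- **Denominator.** SAP 5.1.5.1 defines it for a single 6-month interval only. That section also uses risk sets and censoring for time to first event, but not by satisfaction.
- **Missing data.** SAP 5.2 says "missing data will be excluded and variables will be analyzed using the available observed data". It does not say whether a partly observed multi-year outcome counts as missing or as no event.
- **Derivations.** SAP 5.1.1 leaves variable derivations to a separate specification document.
- **Period.** The objective in SAP 2.2.3 concerns "long-term health outcomes such as, CS-related hospitalization, CS-related emergency room (ER) visits, and mortality over the study period". The protocol synopsis uses the long-term label for what comes after month 6: "Following the month 6 time point, long-term assessments are to include changes in weight".
- **End of observation.** Protocol 5.1.1: "Participation in the study is contingent on continued use of XERMELO". SAP 3.2.7 terminates patients who stop XERMELO, and Protocol 5.1 disables the survey link once the pharmacy reports a status change such as stopping treatment.
- **Potential follow-up.** Protocol 6 allows up to 3 years, but the last patient enrolled gets only the Baseline and first 6-month surveys.
- **Model limitations.** Protocol 10.4.1: "Any statistical models that will be used and the appropriateness and/or limitations of their use will be described in the SAP".

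**The concern.** An ever/never outcome over a whole study is comparable between groups only if the groups are observed for similar lengths of time. Here observation ends with treatment, and Protocol 3.2 records the sponsor's assumption that satisfied patients stay on XERMELO. The exposure may therefore determine how long a patient can report an event.

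If unobserved time is scored as event-free, the group observed longer appears to have more events. If incomplete event-free patients are dropped instead, the group with more early leavers loses more of its non-events and appears to have the higher risk. The same data can then give an odds ratio above or below 1 when no association exists, depending on a rule the SAP does not state.

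It is also unclear whether events in months 0 to 6, before satisfaction was measured, count.

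At stake are the planned whole-period analyses for the exploratory objective. SAP 5.1.5.4 cautions only that p-values are descriptive and that additional analyses depend on data availability. Neither caution concerns follow-up, although Protocol 10.4.1 assigns model limitations to the SAP.

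**Working it through.** **Inputs from the documents.** Month-6 responders: n = 385 (SAP 2.4). Check: 1.96² × 0.5 × 0.5 / 0.05² = 384.16, rounded up to 385; 385 / 0.6 = 641.7, so 642 against the stated 643, an immaterial difference. Potential follow-up: 6 to 36 months (Protocol 6). Two-sided alpha: 0.05 (SAP 5.1.5.4).

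**Assumptions (not in the documents).** No true association; event risk h = 0.10 per 6 months in both groups; potential follow-up equally likely to be 6, 12, ..., 36 months; retention r per interval after month 6 of 90% (satisfied) versus 70% (not); stopping unrelated to events.

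**Set-up.** Let m be the potential intervals after month 6 (0 to 5, equally likely) and K the number observed: P(K = k) = r^k(1 − r) for k < m, and r^m for k = m. Mean observed time is 17.8 versus 13.1 months.

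**Rule 1: unobserved time scored as event-free.** Risk = average over m of E[1 − 0.9^(K+1)].

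| m | r = 0.90 | r = 0.70 |
|---|---|---|
| 0 | 10.00% | 10.00% |
| 1 | 18.10% | 16.30% |
| 2 | 24.66% | 20.27% |
| 3 | 29.98% | 22.77% |
| 4 | 34.28% | 24.34% |
| 5 | 37.77% | 25.34% |
| mean | 25.80% | 19.84% |

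OR = (0.2580/0.7420) / (0.1984/0.8016) = **1.40**.

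- Potential follow-up of 6 to 18 months (m = 0, 1, 2): 17.59% versus 15.52%, OR **1.16**.
- Retention 90% versus 85%: 25.80% versus 24.09%, OR **1.10**.
- Months 0 to 6 not counted (exponent K, m from 1 to 5): OR 1.77.

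**Rule 2: event-free patients who miss any of their own potential follow-up are dropped.** The event-free complete fraction is the average over m of r^m × 0.9^(m+1): 56.65% versus 38.01%. Risks: 25.80/(25.80 + 56.65) = 31.3% versus 19.84/(19.84 + 38.01) = 34.3%. OR = **0.87**.

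**Rule 3: 36-month completers only.** Risk = 1 − 0.9⁶ = 46.9% in both groups, OR 1.00. Those retained are (1/6) × 0.9⁵ = 9.8% and (1/6) × 0.7⁵ = 2.8%.

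**Control.** Equal retention (80% versus 80%) gives OR 1.00 under all three rules, so staggered entry alone does not cause the bias.

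**False rejection at p < 0.05** (normal approximation, 385 patients, nominal 5%). Rule 1: 29% with a 50/50 satisfaction split and 18% at 80/20; 7% at 90% versus 85% retention (50/50). Rule 2: 8% (50/50).

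**With a true hazard ratio of 0.80** (satisfied h = 1 − 0.9^0.8 = 0.081), equal retention gives OR 0.79 under Rule 1. At 90% versus 70%, Rule 1 gives 1.10 and Rule 2 gives 0.68.

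**Time-at-risk alternative.** A complementary log-log model on post-month-6 intervals, in 3,000 simulations per case, gave a hazard ratio of 1.00 to 1.02 with 4% to 5% rejection under no association. It gave 0.79 to 0.81 when the truth was 0.80, with only 11% to 14% power. If an event doubles the odds of stopping in that interval and then goes unreported, it still shows a false hazard ratio of 1.17 at 90% versus 70%.

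**The case against.** Several points against the concern stand.

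- A reader might infer that dependence of follow-up on satisfaction always biases the odds ratio. It does not: 36-month completers give 1.00 if stopping is unrelated to events. But the SAP does not choose that rule, and it discards most patients. It also fails if stopping follows events: with 36 months available to all and 10% versus 30% stopping per interval, doubling the chance of stopping after an event gave OR 2.31.
- A reader might infer that no denominator or scoring rule exists anywhere. The analysis set is stated in SAP 5.1.5.4, interval denominators are in 5.1.5.1, and the separate specification named in 5.1.1 may hold a scoring rule. The documents show only that the whole-period rule is absent from the SAP. That document would not supply the limitations statement that Protocol 10.4.1 places in the SAP.
- More extreme reversals can be constructed, but they need 36 months of potential follow-up for everyone, which Protocol 6 contradicts, or exclusion of event-free patients whose follow-up ended administratively, which no section suggests.
- No document gives retention after month 6; Protocol 3.2 is qualitative. With late recruitment or similar retention the bias is small.
- Under Rule 1 the bias runs against the sponsor's expectation, so it would not create a falsely favourable result. It could still hide a real association.
- The section plans per-interval tests, which are largely free of the problem. It also allows additional or alternative analyses, names Cox models, and treats p-values as descriptive.

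These points limit the size and weight of the concern. They do not supply an adjustment for follow-up in the two committed whole-period analyses.

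**Conclusion.** The point holds for the whole-period chi-square test and logistic model of ER visits and hospitalizations. Neither uses time at risk, and the design makes follow-up that depends on satisfaction plausible. In that case the odds ratio is biased upward if unobserved time is scored as event-free and downward if incomplete event-free patients are dropped: 1.40 and 0.87 at 90% versus 70% retention, with the first shrinking to 1.16 or 1.10 under the milder assumptions above. Event risk, retention and the spread of follow-up are all assumed; only the structure comes from the documents.

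The conclusion does not extend to mortality, which comes through the pharmacies rather than the surveys and is not clearly stated to stop with XERMELO. It does not touch the primary or secondary endpoints. Importance is low to moderate, but the change is worth making before the final analysis.

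**What to change.** In SAP 5.1.5.4:

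1. Make the planned association analysis for ER visits and hospitalizations a time-at-risk model by satisfaction category: discrete-time complementary log-log by 6-month interval, or interval-censored proportional hazards. Set the time origin at the month-6 survey (SAP 5.1.1 sets Day 1 at Baseline), count only later events, and censor at the last completed survey.
2. Keep the per-interval tables.
3. Keep the whole-period table and logistic model as supplementary only. State their denominator, the scoring of event-free patients with incomplete follow-up, and whether months 0 to 6 count.
4. Add the limitations statement that Protocol 10.4.1 calls for. It should say that the supplementary analyses do not correct for discontinuation, and that events in the interval of stopping may go unreported because "Each survey will establish ongoing treatment with XERMELO and continued consent to study participation prior to subsequent data collection".

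A sensitivity analysis for informative censoring is optional; requiring one would be out of proportion here.

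The cost is SAP wording and slightly more programming on data already collected, with methods of a kind the SAP already names (Cox models in 5.1.5.4, interval-censored estimation in 5.1.5.1). The downsides are fewer events because months 0 to 6 are excluded, low power for modest associations, hazard ratios in place of odds ratios, and no recovery of events unreported in the stopping interval.
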